**7.3.14. Study overview**

Visit	Visit 1	Visit 2	Visit 3	Visit 4	Visit 5	Visit 6	Protocol section
Time point	Month 0	Month 1	Month 2	Month 3	Month 6	Month 12	
Informed consent	X						17, Error! Reference source not found.
Inclusion and exclusion criteria	X						Error! Reference source not found., Error! Reference source not found.
Anamnesis and medical examination	X						7.8.2
Demographic data	X						7.8.2
Beverage history	X						7.8.2
SADD	X*				X	X	7.3.1
TLFB	X*	X	X	X	X	X	7.3.2
AUDIT	X*				X	X	8.3.3
DUDIT	X						7.3.3
Motivation questions	X						Error! Reference source not found.
CGI (S and I, respectively)	X ^s				X ^I	X ^I	7.3.5
EQ-5D	X				X	X	7.3.6
Urine sample	X						7.3.7
Blood samples	X	X	X	X	X	X	7.3.7
Documentation of assessment and conventional	X	X	X	X	X	X	Error! Reference source not found..

treatment including drugs							Error! Reference source not found.
Compliance to treatment		X ^a	Error! Reference source not found.				
Safety reporting	X	X	X	X	X	X	7.3.13, Error! Reference source not found.
Randomization	X						7.8.2
TripleA dividend and registration in caregiver portal [#]	X				X		7.8.2
TripleA return [#]					X	X	7.8.8

^a) Refers to baseline

^s) CGI-Severity

^l) CGI-Improvement Scale

^a) Participation in agreed therapy meetings, AA meetings etc

[#]) Only intervention arm. TripleA needs to be calibrated after 6 months use and will therefore be replaced at visit 5.

7.4. Equipment to be used in the clinical study to measure variables

In addition to the study product, laboratory equipment is used in an accredited laboratory for routine analyzes of alcohol metabolites.

7.5. Loss

7.5.1. Loss of patients

The reason why a patient discontinues treatment or study must be documented and these patients must be followed up. Patients who discontinue the study will not be reimbursed. The loss will be reported.

7.5.2. Loss of individual values

Missed blows are discussed with the patient during the visits. If the patient has a plausible explanation for the lack of a single puff, the caregiver can state this in the system, and indicate whether or not there should have been alcohol in the exhaled air at the time in question. A patient who so wishes may submit an extra blood sample to prove that he has been sober during the period when measurement values are missing.

7.6. Test product(s) and comparator(s)

7.6.1. Description of the exposure of the test product (s) or comparative product, if used.

The test product TripleA is used by the patients in the intervention group throughout the study period, a total of 12 months. The patient is instructed to always carry the breathalyzer and the associated mobile phone. SMS notification indicates that it is time to make a measurement. The patient then needs to complete the measurement within 60 minutes.

Measurement can not be done on the patient's own initiative, but only after activation via SMS notification. SMS notifications occur randomly several times a day, which means that the patient does not know in advance when it is time for the next measurement. The caregiver can set a break for night rest when notifications are not sent.

7.6.2. Justification for the choice of comparative product

Not applicable no comparator will be studied.

7.6.3. List of other medical devices or drugs to be used during the clinical study

No other medical devices or drugs will be linked to the study. However, study participants will be allowed to continue or start using other products and medicines in parallel with the study, provided that this is documented in the patient's medical record.

7.6.4.The number of product units used, and justification for this

One TripleA unit per study participant is used at a time. At 6 months, the unit will need to be calibrated and the study participant will then be assigned a new TripleA to not be without when the first one is sent back to Kontigo Care for calibration.

A total of approximately 200 units are estimated to be used within the framework of the study.

7.7. Subjects

7.7.1.Inclusion criteria for selection of subjects

- Patients for whom there is a care commitment for the alcohol program at the Addiction and Neuropsychiatry, Akademiska sjukhuset
- 18 years or older
- Meets at least 2 of the criteria for addiction / substance syndrome according to DSM-5
- Ability to understand and communicate in Swedish
- Ability to handle the technical equipment used in the study (breathalyzer + smartphone)
- Has a fixed point (accommodation, night rest place to charge the phone)

7.7.2.Exclusion criteria for selection of subjects

- Schizophrenia
- Substance syndrome related to substances other than alcohol and nicotine
- Impaired lung function (not able to achieve adequate exhalation volume for breathalyzer function)
- The patient is cared for within the framework of LVM
- Unsuitable to participate in the study according to the examiner's assessment
- Has not consumed any alcohol during the 4 weeks that baseline Time Line Follow Back refers to.
- Normalized CDT and PEth values in blood samples taken at visit 1.

7.7.3.Criteria and procedures for removing subjects from the study or suspending their participation

Substance syndrome related to substances other than alcohol and nicotine: Screening with urine sample and DUDIT is done at inclusion. The test result does not have to be available before the subject is included in the study, but should a positive screening test be reported, the subject should be removed from the study. No further samples are taken within the framework of the study.

Should the patient lose or otherwise lose the test product, it can be replaced (a limited number of times) and the patient does not need to be removed from the study if alcohol consumption is reported during the days when the measurements could not be performed and blood tests are performed to determine a new level of PEth / CDT . Phones that have fallen into the wrong hands or are misused in other ways can be deactivated by Kontigo Care. Contact Kontigo Care should this occur.

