7.3.7. Biological samples (blood and urine)

Samples are ordered via the medical record system, taken and handled according to regular clinical routine. Patients are instructed to leave the samples some week before the visits, so that test results are available for the visit.

For sampling instructions, refer to the latest updated versions on the Academic Laboratory's website.

Urine samples for drug screening usually include amphetamine, benzodiazepines, burprenorphine, cannabis, cocaine, methadone metabolites, opiates. Verification analysis in the event of a positive result on a urine dipstick is performed if clinically relevant

Time: Done at visit 1

Phosphatidylethanol (PEth) is analyzed at Karolinska Laboratory. The concentration of PEth-16:0/18:1 is given in the unit $\mu\text{mol} / \text{L}$. The PEth level in the blood reflects the alcohol consumption of recent weeks. PEth-16:0/18:1 values lower than $0.05 \mu\text{mol} / \text{L}$ indicate no or low sporadic alcohol consumption. Values between $0.05-0.30 \mu\text{mol} / \text{L}$ speak for regular moderate consumption, but even occasional very large intakes of alcohol can probably give measured values in this range.

Time: Made at each visit

Low carbohydrate transferrin (CDT) shows alcohol-induced change in the glycosylation pattern of transferrin, which is measured in serum samples. CDT is used as a marker to demonstrate regular alcohol consumption and «risk use / abuse», where the measured value reflects the intake during the last weeks - the month. Single major alcohol intakes do not affect CDT levels.

Analyzed at the Academic Laboratory and reported in%. Reference interval $<2.0\%$.

Time: Made at each visit

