9.2. Sample size, significance level and statistical strength

The primary endpoint is the proportion of patients who do not have heavy drinking days during a 4-week period after 12 months from baseline. Assuming that the proportion is 30% in the control group and you want to be able to detect a difference of 30% between the TripleA and the control group, 42 patients are needed per treatment group to achieve a strength of 80% with a double-sided test of 5% significance level. Assuming that the proportion of patients who do not complete the study is about 20%, a total of 106 patients need to be randomized, ie 53 per group.

Expected loss

The drop-out rate in alcohol studies is usually quite large.

At inclusion, the patient is asked to provide at least one contact person that the study staff can contact if the patient is absent from agreed meetings, interrupts treatment and / or stops blowing. Patients who do not wish to continue their treatment should be informed that they are welcome to continue using TripleA and / or alcohol, or otherwise report their alcohol consumption, as this is valuable information for the study. If the patient wants to stop the study completely, the study staff should at least ask the question "how many standard glasses have you drunk the most in one day since we were last seen?". This gives the opportunity to assess whether there has been a heavy drinking day or not.

A certain loss of patients during the course of the study is expected. Three types of missing data can be identified.

1. Patients who choose to discontinue treatment and study participation.
2. Patients who choose to discontinue treatment but who continue to provide information on alcohol intake (i.e. remain in the study)

Patients who continue treatment but who do not provide complete information on alcohol intake.

4. Patients who miss occasional visits.

All efficacy evaluations will be performed on two analysis populations, a population consisting of all randomized patients contributing efficacy data from at least one baseline visit (ITT) and a population consisting of all patients who completed the study according to the protocol (PP).

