9.	Hur ofta under senaste året har du haft skuldkänslor eller dåligt samvete på grund av att du använt droger?	Aldrig 	Mer sällan än en gång i månaden 	Varje månad 	Varje vecka 	Dagligen eller nästan varje dag 		
10.	Har du eller någon annan blivit skadad (psykiskt eller fysiskt) på grund av att du använt droger?	Nej 	Ja, men inte under det senaste året 	Ja, under det senaste året 				
11.	Har en släktling eller vän, en läkare eller sjuksköterska, eller någon annan oroat sig över att du använder droger eller sagt till dig att du bör sluta med droger?	Nej 	Ja, men inte under det senaste året 	Ja, under det senaste året 				

DROGLISTA

(OBS! EJ ALKOHOL)

Cannabis	Amfetamin	Kokain	Opiater	Hallucinogener	Lösningsmedel	GHB och övriga
Marijuana	Metamfetamin	Crack	Rökheroin	Ecstasy	Thinner	GHB
Hasch	Fenmetralin	Freebase	Heroin	LSD	Trikloreyten	Anabola steroider
Hascholja	Khat	Kokablad	Opium	Meskalin	Bensin	Lustgas
	Betelnöt			Peyote	Gas	Amylnitrat (poppers)
	Ritalina			PCP	Solution	Antikolinergika
				Psilocybin		
				DMT	Lim	

TABLETTER – LÄKEMEDEL

Tabletter räknas som droger när du tar

- läkemedel mer eller oftare än läkaren sagt att du ska göra det
- tabletter för att du vill ha kul, må bra, bli "hög", eller undrar vad du får för effekt av dem
- tabletter som du fått av en släkting eller vän
- tar tabletter som du köpt "svart" eller stulit

SÖMNMEDEL/LUGNANDE MEDEL

Alprazolam	Halcion	Sobril
Apodorm	Heminevrin	Sonata
Apozepam	Iktorivil	Stesolid
Diazepam	Imovane	Stilnoct
Dormicum	Mogadon	Temesta
Fenemal	Nitrazepam	Triazolam
Flunitrazepam	Oxascand	Xanor
Fluscan	Rohypnol	Zopiklon

SMÄRTSTILLANDE

Actiq	Durogesic	OxyNorm
Cocillana-Etyfin	Fentanyl	Panocod
Citodon	Ketodur	Panocod forte
Citodon forte	Ketogan	Paraflex comp
Dexodon	Kodein	Somadril
Depolan	Maxidon	Spasmofen
Dexofen	Metadon	Subutex
Dilauidid	Morfin	Temgesic
Distalgesic	Nobigan	Tiparol
Dolcontin	Norflex	Tradolan
Doleron	Norgesic	Tramadol
Dolotard	Opadol	Treo comp
Doloxene	OxyContin	

Tabletter räknas INTE som droger när du fått dem utskrivna av läkare och du tar dem i rätt mängd.

Bilaga F

MÅL OCH MOTIVATION

Målsättning

[figure not shown]
Att bli alkoholfri
 Att minska alkoholkonsumtionen

[figure not shown]

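### A positive urine drug screen can remove patients who are already randomised, and the plan does not secure their month-12 outcome

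*Combined protocol and SAP*

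**What the plan says.** **Order of events.** Section 7.8.2 (Visit 1) lists consent, the eligibility check, blood samples, the urine drug test and then randomisation, in which the care provider opens the next code envelope. The overview in 7.3.14 puts all of these at month 0. Section 7.7.4 defines inclusion as signed consent.

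**Removal rule.** Section 7.7.3 states that the drug-screen result need not be available before inclusion, and that "should a positive screening test be reported, the subject should be removed from the study". It adds that no further samples are then taken in the study.

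**Exclusion criteria.** Section 7.7.2 excludes a substance syndrome involving substances other than alcohol and nicotine. It also excludes "Normalized CDT and PEth values in blood samples taken at visit 1".

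**Screening.** Under 7.3.7 the urine panel usually includes benzodiazepines and opiates, among others. On confirmation it says: "Verification analysis in the event of a positive result on a urine dipstick is performed if clinically relevant". The same section tells patients to leave samples about a week before visits so that results are ready. Section 17.5, however, says that drug screening will not be done within the study. The DUDIT form (Bilaga E) tells patients that correctly used prescribed tablets do not count: "Tabletter räknas INTE som droger när du fått dem utskrivna av läkare".

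**Follow-up and analysis.** For patients who discontinue treatment or study, 7.5.1 says "these patients must be followed up"; it does not mention patients whom the study removes. Section 9.2 defines ITT as all randomised patients with baseline efficacy data, treats it as primary, and lists four types of missing data.

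**The concern.** The urine sample is taken before allocation, but its result may arrive afterwards. A patient can then be allocated, start the trial and be taken out of it for a reason unrelated to the outcome. The primary endpoint is read from TLFB for the four weeks before the month-12 visit (7.2.1), so a patient with no further visits has no observed primary outcome.

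Two features add to this. First, the trigger is a positive screening test, whereas the criterion it serves is a substance syndrome. Section 7.6.3 allows other medicines during the study, and the panel covers drug classes that can be prescribed. A patient who meets no exclusion criterion could therefore be removed. Second, the trial is open (7.1.1) and confirmation of a positive result is optional. If that choice is made after the envelope is opened, the allocated arm could influence who is removed.

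At stake are avoidable missing primary outcomes in a trial of 106 patients, and possibly some power.

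**Working it through.** **Step 1. Can removal follow randomisation?** The waiver in 7.7.3 concerns inclusion, which 7.7.4 ties to consent, so it does not itself mention randomisation. But 7.8.2 places sampling and the envelope in one visit, estimated at about 1 hour (7.7.6), and no section requires the result before the envelope. A patient handled exactly as written can be randomised first and removed later.

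**Step 2. What happens in the analysis?** A removed patient with baseline TLFB belongs to ITT under 9.2. The listed missing-data types are: patients who choose to leave treatment and study; patients who choose to leave treatment but still report intake; patients who stay but report incompletely; and patients who miss occasional visits. Removal by the study is none of these. Multiple imputation would presumably apply, but the plan does not say so.

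**Step 3. Reproduce the sample size.** Inputs from 9.2: "Assuming that the proportion is 30% in the control group"; "detect a difference of 30% between the TripleA and the control group"; and "42 patients are needed per treatment group to achieve a strength of 80% with a double-sided test of 5% significance level". With p1 = 0.30, p2 = 0.60 and mean p = 0.45, pooled variance and no continuity correction:

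n = [1.96 × √(2 × 0.45 × 0.55) + 0.8416 × √(0.30 × 0.70 + 0.60 × 0.40)]² / 0.30²

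= (1.379 + 0.565)² / 0.09 ≈ 42 per group.

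Allowance for 20% non-completion: 42 / 0.80 = 52.5, rounded up to 53 per group, or 106 in total. Both stated figures reproduce. Since 53 × 0.80 = 42.4, the planned power is 80.4%.

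**Step 4. Add removals.** The documents give no rate of positive screens, so the share r is an assumption. If removals come on top of the 20%:

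observed per arm = 53 × 0.80 × (1 − r)

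power = Φ{[0.30 × √n − 1.96 × √(2 × 0.45 × 0.55)] / √(0.30 × 0.70 + 0.60 × 0.40)}

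| r (assumed) | Removed of 106 | Observed per arm | Power | Randomised total needed to keep 42 per arm |
|---|---|---|---|---|
| 0% | 0 | 42.4 | 80.4% | 106 |
| 5% | 5.3 | 40.3 | 78.3% | 112 |
| 10% | 10.6 | 38.2 | 76.0% | 118 |
| 15% | 15.9 | 36.0 | 73.5% | 124 |

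If the 20% was meant to include removals, the first row applies and no power is lost. The removed patients' outcomes are still missing in that case.

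**The case against.** The strongest reply is that the plan may already contain the loss. The 20% in 9.2 is the share who do not complete the study, and a removed patient is a non-completer. Removed patients also stay in ITT by definition, and missing values there are multiply imputed. This stands as far as it goes: the power loss is conditional. It does not explain why outcomes that could be collected should be given up.

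A reader might infer several stronger points that the documents do not support.

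- **That ITT itself is broken.** It is not: a removed patient with baseline TLFB remains in the ITT population. The gap is a missing outcome and an unstated rule for handling it.
- **That CDT and PEth results also remove randomised patients.** The waiver and the removal rule in 7.7.3 cover only the drug screen. The eligibility check in 7.8.2 and the advance sampling in 7.3.7 suggest that these results should be known in time. The visit 1 list, with blood taken after consent and before the envelope, suggests otherwise. The timing needs reconciling, but late exclusion on these markers is only an inference.
- **That removal ends all sampling, against 7.5.1.** The sentence on no further samples closes a paragraph about drug screening and may mean only that no more drug tests are done. Section 7.5.1 does not exempt removed patients; it simply does not say whether it covers them.
- **That an unblinded caregiver decides on verification.** Section 7.3.7 names no decision-maker, and a dipstick result could be available before allocation. Because the urine is taken before randomisation, removal should not differ by arm if the rule is applied uniformly.

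**Conclusion.** The point holds in a limited form. As written, the plan allows a randomised patient to be removed on a positive drug screen. It then leaves open whether the month-12 outcome is collected and how its absence is handled. The trigger is wider than the exclusion criterion it serves.

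The main consequence is avoidable missing data in the primary analysis. Its size cannot be computed from the documents. Under assumed removal of 5% to 15% beyond the 20% allowance, about 5 to 16 of 106 patients would go and power would be about 78% to 74%. If the allowance already includes them, the loss of power is nil. A reader might go further and infer biased removal between arms. The open design and optional verification make that possible, but nothing in the documents shows it.

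**What to change.** In 7.7.3, for patients already randomised, replace removal from the study with a rule to this effect: ineligibility discovered after randomisation is recorded as a protocol deviation and excludes the patient from PP only; the patient stays in ITT, and study visits and TLFB continue to month 12. Whether device use continues is a clinical matter for the investigator.

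In 7.5.1, say that the follow-up rule covers these patients. In 9.2, say how their data enter the primary analysis. This matters because 9.2 treats values collected after treatment interruption as missing and imputes them. Without a statement, an outcome collected under the new rule could still be set aside.

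Reconcile 7.3.7, 7.5.1, 7.7.2, 7.7.3, 7.8.2 and 17.5 on three matters: when the urine and CDT/PEth samples are taken, whether their results are needed before randomisation, and whether drug screening is part of the study. State also how a positive screen relates to the substance-syndrome criterion.

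The cost is protocol wording, continued follow-up of the few patients concerned, and some ineligible patients in ITT. Label: cheap improvement. Holding the envelope until laboratory results arrive would also close the gap. But consent, sampling, allocation and device training now share one visit of about an hour, so waiting would probably need a second contact within the 4-month recruitment period. That option is not clearly cheap.

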7.2. Efficacy endpoints

7.2.1. Primary efficacy endpoint

Proportion of patients who do not have heavy drinking days

Clinically relevant for treatment focused on risk reduction is that patients do not have heavy drinking days. The measurement tool will be TLFB (see Appendix C) where the number of days with large consumption over a four-week period is calculated.

Heavy drinking days are the same as days with heavy consumption, which means consumption of 4 or more standard glasses of alcohol per day for women and 5 or more standard glasses of alcohol per day for men.

How to determine the TLFB at baseline is stated in section 8.1.2. Follow-up TLFB is then made at each visit. The primary measure of effectiveness is the difference between the treatment arms in the proportion of patients who do not have heavy drinking days during the 4-week period preceding the 12-month visit.

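### Section 7.7.3 implies that losing the device can end study participation, which can happen only in the TripleA arm, and the plan gives no analysis rule for patients removed this way

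*Combined protocol and SAP*

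**What the plan says.** Section 7.7.3 sets out the criteria for removing subjects. It allows a lost device to be replaced, up to a number of times that is not given. It adds that "the patient does not need to be removed from the study if alcohol consumption is reported during the days" when measurement was not possible and blood is tested for a new PEth and CDT level. It does not say what happens when these conditions are not met.

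Other sections bear on this:

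- **7.6.1:** "The test product TripleA is used by the patients in the intervention group throughout the study period". Controls have no device.
- **7.2.1:** the primary measure is the difference between arms in "the proportion of patients who do not have heavy drinking days during the 4-week period preceding the 12-month visit". It comes from the TLFB calendar and needs no device data.
- **7.5.1:** "The reason why a patient discontinues treatment or study must be documented and these patients must be followed up".
- **9.2, Expected loss:** patients who stop treatment are invited to keep reporting their drinking, "as this is valuable information for the study". Even those leaving completely are asked for their highest one-day intake.
- **9.2, missing data:** type 1 is "Patients who choose to discontinue treatment and study participation", and these values are multiply imputed. Values collected after treatment interruption (type 2) are set to missing and imputed in the main ITT analysis. Missed visits (type 4) are also imputed. Removal under 7.7.3 is not among the listed types.

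**The concern.** A condition for staying in the study has little purpose unless failing it can lead to removal. Here it would operate after randomisation, in one arm, and depend on whether the patient accounts for drinking on unmeasured days. Neither the lost device nor the gap prevents the site from completing the TLFB at month 12, so removal would give up a primary outcome that could still be collected.

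Such removals are unlikely to be unrelated to drinking. The protocol itself treats unexplained gaps as a possible sign of it: section 7.3.2 wants missed measurements to correspond to more than zero glasses, section 9.1.2.2 gives relapse as one explanation for missed tests, and section 7.8.11 warns of concealment. If removed patients do worse than the imputation model predicts, the TripleA proportion in ITT is too high, with no matching mechanism among controls. The per-protocol set would lose the same patients. At stake is a possible arm-specific bias in the primary comparison.

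**Working it through.** **1. The plan's own figure.** Section 9.2 assumes 30% in controls and a difference of 30 points (so 60%), with 80% power and a two-sided 5% level. With pooled variance and no continuity correction:

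n = [1.96 × √(2 × 0.45 × 0.55) + 0.842 × √(0.30 × 0.70 + 0.60 × 0.40)]² / 0.30² = 42 per group.

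42 / (1 − 0.20) = 52.5, so 53 per group and 106 in total. The stated sample size reproduces, and nothing below changes it.

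**2. What happens to a removed patient.**

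| Situation | 12-month TLFB | ITT | PP |
|---|---|---|---|
| TripleA patient removed under 7.7.3 | not collected, if removal ends the visits | not classified in 9.2; imputation is the most likely reading | excluded |
| Control still in treatment who attends visit 6 | collected | used as observed | included if otherwise per protocol |
| Patient in either arm who leaves, or misses visit 6 | missing | imputed (type 1 or 4) | excluded if the study was not completed per protocol |

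The difference between arms lies in the first two rows only.

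**3. Size.** The inputs other than 53, 30% and 60% are assumptions; the documents give neither the number of device losses nor the imputation model. Let k of 53 TripleA patients be removed, let q be their true success rate, and let them be imputed at the rate r of retained TripleA patients. Control data are taken as complete. The overstatement of the TripleA proportion is

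bias = (k / 53) × (r − q).

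*No true effect (30% in both arms), q = 0.* Then r = 0.30 × 53 / (53 − k), and the bias reduces to 0.30 × k / (53 − k):

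- k = 3: 0.90 / 50 = 1.8 points
- k = 5: 1.50 / 48 = 3.1 points
- k = 8: 2.40 / 45 = 5.3 points

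*Retained patients succeed at 60%, q = 0.* The bias is 0.60 × k / 53:

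- k = 3: 3.4 points
- k = 5: 5.7 points
- k = 8: 9.1 points

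*No true effect, q = 15%.* The bias is 0.15 × k / (53 − k), or 0.9, 1.6 and 2.7 points.

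*Removed patients no worse than the rest (q = r).* The bias is zero for every k.

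**4. Effect on the two-sided error, no true effect, q = 0.** The comparison is a pooled z-test of 53 controls at 0.30 against 53 − k retained TripleA patients at rate r. With d = r − 0.30, s0 the pooled and s1 the unpooled standard error, the rejection rate is Φ((d − 1.96 s0)/s1) + Φ((−d − 1.96 s0)/s1). For k = 5: r = 0.331, d = 0.031, s0 and s1 both about 0.093, giving 6.3%. For k = 3 and 8 it is 5.5% and 8.7%, against a nominal 5%.

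**The case against.** The strongest reply is that 7.7.3 mandates no removal. The sentence is permissive, the English is a rough translation, and it can be read as a retention provision: replace the device, fill the gap with self-report and blood tests, keep the patient. TLFB and PEth/CDT are already taken at every visit in both arms, and reporting consumption can include reporting zero. A patient who attends and reports largely meets the conditions, and one who does neither would often have missing data as a control too. The group affected by the arm-specific rule may therefore be small. This stands as a limit on size. It does not remove the ambiguity, because the section is headed as criteria for removal and leaves the unmet case open.

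A reader might infer something stronger: that TripleA relapsers are removed and replaced by imputed successes while comparable controls keep their observed result. The documents do not support that:

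- Nothing says that patients who lose a device are relapsers; that is plausible only.
- Type 1 covers patients who choose to leave, so imputation of removed patients is an inference. The imputation model is not specified, and one using earlier TLFB or biomarker values could predict worse outcomes for them.
- Controls who leave or miss visit 6 are imputed as well.

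The larger figures also need care. The 3.4 to 9.1 points take every removed patient as a failure and the imputed rate as the full planned 60%. Eight of 53 is 15%, about three quarters of the whole planned loss of 20%.

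It could also be said that 7.5.1 softens the problem by requiring follow-up. It does if it governs, but it gives no method, and removal from the study points the other way.

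**Conclusion.** The point holds as an implied removal after randomisation that can act in one arm only, conflicts with 7.5.1 and with the aim stated in 9.2, and has no analysis rule. It is not shown that the plan is biased in favour of TripleA: that direction requires removed patients to do worse than the imputation predicts.

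Under the assumptions shown, with every removed patient a failure, 3 to 8 removals of 53 would add 1.8 to 5.3 points with no true effect, or 3.4 to 9.1 points with retained patients at 60%, against a planned difference of 30 points. With removed patients no worse than the rest the bias is zero. The effect is likely to be small unless device losses are frequent. The change is worth making because it costs almost nothing and closes the route altogether. It is a cheap improvement.

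**What to change.** Two text changes are needed; one sentence in 7.7.3 would not be enough.

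- **Section 7.7.3:** state that loss of the device affects device data only and is not a reason for removal from the study, and that scheduled visits, TLFB and blood samples continue to month 12.
- **Section 9.2, missing data:** state that TLFB values collected after device loss are used as observed in ITT. Without this, device loss could be taken as treatment interruption, and the collected values would be set to missing and imputed.

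Sections 7.5.1, 7.7.3 and 9.2 should then be reconciled so that they give one account of who is followed and how their data are analysed. Whether and how often a device is replaced stays with the sponsor.

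The cost is text in two sections and continued follow-up of a few patients at visits already scheduled. The sample size does not change.
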